Starting in Year 2, in a 2-arm RCT, we will pilot the *SnappyHour* intervention versus a control group (n=50-52 per group) among EAs with HID (balanced on sex and age group). Screened, eligible participants will complete baseline measures, their assigned condition for 8 weeks, a 2-month (after intervention-start) post-test after the active intervention period (to measure intervention acceptability, changes in outcomes during the intervention period, and mechanisms of change), and a 4-month (after intervention-start) outcomes assessment.

Enrollment: Target enrollment is 102 EAs (approximately 50% males and 50% females) between the ages of 18-25. We will conduct a 2-arm pilot RCT of the Snapchat intervention versus a control group (n=50-52 per group) among EAs with HID (balanced on sex and age group). We will enroll participants in 3-4 waves to allow breaks between 8-week intervention periods for staff.

Recruitment and Study Procedure. Recruitment and enrollment procedures will follow those used in Aim 1 above. To ensure representation of both sexes we will recruit approximately 50% males and 50% females. Using a similar approach to the National Epidemiologic Survey on Alcohol and Related Conditions (NESARC), we will attempt to oversample minorities who are African American and Hispanic (~20%). Thus, we expect approximately 67% Caucasian, 20% African American, 3% Asian, 1% Native American/Alaskan Native, 1% Hawaiian/Pacific Islander, and 8% more than 1 race and 20% Hispanic.

Study participants will be recruited via SM advertisements that appears on social media applications (e.g., primarily Snapchat, but Instagram, Facebook etc., as needed). Ads will be targeted to U.S users ages 18-25. When users swipe up or click on an advertisement, they will be redirected to a privacy notice (as required by Snapchat, our primary recruitment modality), and subsequently, a screening informed consent page. After indicating their agreement to the consent online (with a waiver of parental consent for states with age of majority >18 and a waiver of documentation of consent given our online procedures) and completing a captcha (to protect against bots), participants will complete a ~5-min eligibility survey.

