From the pool of eligible and verified participants, study staff will select participants to receive an invitation to continue to the next part of the study (baseline). Screening items will be used to select participants representing a variety of characteristics (e.g., gender, race/ethnicity) to ensure that the intervention is widely acceptable among individuals in the study's target age group. Selected, verified participants will be invited to view and agree to the RCT consent in Qualtrics, followed by an online baseline survey. Selected participants will receive an email containing a link to the consent and baseline survey in Qualtrics. Participants who indicate that email is not their preferred method of communication will receive a text/social media notification (depending on their preferred contact method) directing them to the email with their consent and survey link. We will send reminders via different contact methods (e.g., email, private message on social media, text) to encourage completion of this survey and completion of study enrollment.

Those who complete baseline measures will be randomized to their assigned condition for 8 weeks, and will later be asked to complete a 2-month post-test after the active intervention period, and a 4-month outcomes assessment. Compensation at baseline will be a \$35 electronic gift card (e.g., Amazon.com, Target, etc.) for participants who complete all baseline activities. Compensation will be a \$35 electronic gift card for the 2-month post-test and a \$40 electronic gift card for the 4-month follow-up.

Inclusion/Exclusion Criteria. For screening, participants must: be age 18-25, reside in the U.S., be able to read English, view, and click on a social media ad. Eligibility criteria for baseline and randomization is self-reported past-month HID (using an item based on MTF¹⁴⁴) and regular Snapchat use (at least 3 days/week). Participants will be excluded if they fail identity verification (see prior studies^{132,133}) based on: 1) IP addresses, 2) survey time completion, 3) repeat attempts, and 4) survey responses. Aim 1 participants are excluded from Aim 2.

Randomization and Consideration of Key Biological Variables. Randomization to conditions will be balanced based on sex and age (18-20, 21-25 years) using urn randomization in blocks of 4. After completing the baseline survey, participants will be informed which condition (intervention, control) they were randomized into via Qualtrics.

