We will provide documentation of IRB approval for all study procedures prior to beginning screening participants.

- 11. Provide the analysis plan including the power calculation(s). There should be discussion of any planned interim and/or futility analyses, including adjustments for allocating "alpha" on "multiple looks" at the data.**

Specific Aim 1. Intervention development will consist primarily of identifying preferences for content delivery and content with superior ratings, and thus will not involve formal statistical inference. We will conduct descriptive analyses of participants' data regarding preferences, leading to refinements in intervention content.

Specific Aim 2. Analyses pertaining to primary outcomes of feasibility and acceptability of the intervention are primarily descriptive in nature (e.g., % completing the assigned intervention condition, % engaging in Snapchat messaging, ratings of intervention satisfaction). To examine other outcomes related to estimating intervention efficacy, in Aim 2, randomized participants will be included in intent-to-treat analyses, regardless of engagement. By design, groups will be balanced on sex and age; we will validate randomization by evaluating covariate balance between groups. If significant differences that could confound treatment effect estimates emerge, we will adjust for those variables or stratify analyses.

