Testing for Intervention Effects. We will first compare groups outcomes of HID frequency and alcohol-related consequences using basic two-sample comparisons, operating on the pre-post differences (e.g., 4M-Baseline) to test for treatment effects. Our first choice will be a two-sample *t*-test to compare the pre-post differences between groups; considering non-parametric alternatives as needed. We will use generalized linear mixed models (GLMMs) to jointly study the 2M and 4M outcomes while adjusting for correlations between data points (e.g. repeated measurements on individuals). While baseline adjustment is important for guarding against regression to the mean in RCTs, such adjustment at every time point may overestimate the treatment effect when there are multiple follow-ups. Baseline adjustment at only the first follow-up (2M in this case) corrects this overestimation while also guarding against regression to the mean, which will be our approach. Within this framework, the treatment effect is estimated by the treatment group indicator in the regression model. We will conduct exploratory sub-analyses of whether the intervention effect is accumulating or weakening over time, by including time-by-group interactions. If we ascertain the need, we will control for confounders through their inclusion in the model as covariates. Overall, this approach is effectively the same as the ANCOVA method of RCT analysis, but modified to account for multiple follow-ups and possibly inhomogeneous treatment effects (e.g. time-varying or modified by other factors, see secondary aims, below). Our initial specification will be a linear mixed effects model (with Gaussian error distribution) with only a random intercept to capture within-individual dependence, but we will scrutinize this choice by examining model diagnostics. If we ascertain the need, we will examine other distributional choices (e.g., Poisson, Negative Binomial) and more complex random effects structures (e.g., autoregressive). **Effect Size Estimation:** This pilot will provide critical data necessary to inform power analyses for a later efficacy trial. While effect sizes from pilot studies can have large standard errors and be unstable, we can use pilot data to estimate point estimates and confidence intervals for treatment effect sizes using the R package MBESS. The effect size of choice will be the standardized regression coefficient corresponding to the treatment group indicator in a model adjusted for the baseline measurement, which will have the same interpretation as the standardized mean difference (commonly referred to as Cohen's D). This analysis will provide a basis for calculating the minimal sample size required for a fully powered study while accounting for uncertainty in the effect size estimate.

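### Sex and age group balance the randomisation but are not pre-specified covariates in the mixed model or the effect-size model (minor; exploratory outcomes only)

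*Combined protocol and SAP*

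**What the plan says.** Aim 2 Methods: Pilot RCT describes the two arms as "balanced on sex and age group". The section Randomization and Consideration of Key Biological Variables gives the age bands (18-20 and 21-25) and an urn scheme in blocks of 4. DSMP item 11, Specific Aim 2, repeats the point: "By design, groups will be balanced on sex and age; we will validate randomization by evaluating covariate balance between groups". It then gives the rule for adjustment: "If significant differences that could confound treatment effect estimates emerge, we will adjust for those variables or stratify analyses". No test or significance level is attached to that rule.

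Under Testing for Intervention Effects, the first comparison is a two-sample t-test on change from baseline. The main model is a mixed model, initially Gaussian with a random intercept only. On the use of baseline it says: "Baseline adjustment at only the first follow-up (2M in this case) corrects this overestimation while also guarding against regression to the mean". On the estimate it says: "Within this framework, the treatment effect is estimated by the treatment group indicator in the regression model". A further clause lets confounders be added as covariates if the investigators judge this necessary, and names no variable.

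Under Effect Size Estimation, the quantity reported is the "standardized regression coefficient corresponding to the treatment group indicator in a model adjusted for the baseline measurement". Its purpose is stated: "This analysis will provide a basis for calculating the minimal sample size required for a fully powered study".

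Neither model lists sex or age group. Under Other exploratory analyses they appear as example moderators, through interactions with treatment, and in a test of differences in engagement.

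**The concern.** Balancing on a factor removes its variation from the treatment comparison. A model that leaves the factor out keeps that variation in the residual, so the reported standard error describes a less well balanced trial than the one that was run. The usual remedy is to put the balancing factors in the model from the start.

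The two conditional rules do not do this. They look for imbalance or confounding, and the reason to include sex and age group is neither. Because the design balances them, a rule triggered by imbalance will almost never pick them.

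At stake is some precision in the exploratory efficacy analyses, and in the effect-size interval that will be used to size the next trial. Whether two obvious covariates are used is also left open until the data have been seen.

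**Working it through.** **1. The plan's own figure.** Power Analysis states more than 80% power for D above 0.56 at one time point with 50-52 per group. Alpha is not stated; 0.05 two-sided is assumed. With power = Φ(D / (s·√(2/n)) − 1.96) and s = 1:
- n = 50: Φ(0.56/0.200 − 1.96) = 80.0%
- n = 51: Φ(0.56/0.198 − 1.96) = 80.7%
- n = 52: Φ(0.56/0.196 − 1.96) = 81.5%

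The noncentral t gives 79.2/80.0/80.7%. The stated figure reproduces to rounding.

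**2. Would the imbalance rule select these factors?** Taking a chi-square test at p < 0.05 (assumed), sex or age group triggered in 0 of 5,000 simulated allocations with permuted blocks of 4 within sex-by-age strata. With an urn within strata the count was 9 of 5,000 (0.18%). In practice, no.

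**3. Effect-size model.** Let R² be the share of outcome variance left after baseline adjustment that sex and age group explain. The documents give no value. The excess in the standard error is 1/√(1−R²) − 1:
- R² = 0: 0%
- R² = 0.01: 0.5%
- R² = 0.05: 2.6%
- R² = 0.10: 5.4%

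A simulation agrees (20,000 trials per cell). Its assumptions are n = 102, both factors split 50/50, permuted blocks of 4 in four strata, baseline-outcome correlation 0.5, true effect 0.5 SD, complete follow-up, and factors **independent of baseline**:

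| R² | Mean SE without / with factors | True size of 5% test without / with | Power without / with |
|---|---|---|---|
| 0 | 0.1719 / 0.1720 | 4.9% / 4.9% | 81.7% / 81.7% |
| 0.01 | 0.1720 / 0.1712 | 4.7% / 4.9% | 81.7% / 81.9% |
| 0.05 | 0.1721 / 0.1677 | 4.3% / 4.8% | 82.2% / 83.5% |
| 0.10 | 0.1721 / 0.1632 | 4.0% / 5.2% | 83.0% / 85.7% |

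**4. The same model when the factors also act at baseline.** Suppose sex and age group explain a share m of variance at every visit, with baseline-outcome correlation 0.5. The squared partial correlation given baseline is (0.5·√m)² / (0.75·(1−m)) = m / (3(1−m)).
- m = 0.02: residual R² = 0.02/2.94 = 0.007, excess 0.3%
- m = 0.05: residual R² = 0.05/2.85 = 0.018, excess 0.9%
- m = 0.10: residual R² = 0.10/2.70 = 0.037, excess 1.9%

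Adjusting for baseline already absorbs much of a stable effect.

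**5. Mixed model.** Baseline enters only at 2 months, so the 4-month residual keeps more of the factor variance. Under the step 3 assumptions, with a 2M-4M correlation of 0.5, the mean standard errors are 0.1562/0.1509 at R² = 0.05 (3.5% too wide) and 0.1564/0.1451 at R² = 0.10 (7.8%). With a 2M-4M correlation of 0.7 the excess is 2.7% and 5.6%. Under the stable-effect assumption of step 4, a smaller simulation (1,200 runs per cell, n = 104) gave about 0.9/2.6/5.3% at m = 0.02/0.05/0.10.

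**6. Effect of the change on the planned power.** With s = √(1−R²), n = 51 and D = 0.56, power is 80.7% at R² = 0, 82.7% at 0.05 and 84.6% at 0.10. In a simulation at one time point with no baseline term, power without the factors was 80.3/80.9/81.4% at those R² values, so omission does not take power below the plan.

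**The case against.** The plan is not silent. Its discretionary clause would allow sex and age group into the mixed model, and the moderation models, fitted in the usual way, contain their main effects. Both points are true. But the clause is aimed at confounders and commits to nothing, and the moderation models are separate from those that give the overall treatment effect and the effect size.

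The size is also open to challenge. The larger effect-size-model figures assume that the factors act on follow-up drinking but not on baseline drinking. A stable effect on level is more natural, and the excess is then about 2% or less for m up to 0.10. If the factors explain nothing beyond baseline, the gain is nil. This objection stands and limits the point.

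The scope is limited too. In the change-score t-test a stable sex or age effect cancels, so these figures do not apply there. They rest on linear Gaussian models. The plan allows Poisson or negative binomial models if diagnostics call for them, and those are not covered.

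A reader might infer that leaving out the balancing factors biases the treatment effect or produces false positives. Under the initial linear specification it does neither: the test is slightly conservative. A reader might also infer that the trial is underpowered as a result. The Power Analysis treats the target as a plain comparison of two means, so it never counted on this gain.

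**Conclusion.** The point holds as a minor, free improvement. The trial balances on two factors that its mixed model and effect-size model do not pre-specify, and the conditional rules would almost never bring them in. The consequence is standard errors that are somewhat too wide, by an amount the documents do not allow one to fix. For the effect-size model, a plausible range runs from nothing to about 2% under a stable effect, and to about 5% if the factors are unrelated to baseline. The mixed model may lose somewhat more.

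These figures assume about 102 participants, complete follow-up, Gaussian outcomes, a baseline correlation of 0.5 and tight balance within strata. The randomisation section does not fully define the urn. An urn within strata gave similar conservatism (true size 3.8% in the effect-size model and 3.7% in the mixed model at R² = 0.10), but a looser scheme would give less. The primary feasibility and acceptability outcomes are descriptive and unaffected.

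**What to change.** In DSMP item 11:
- Pre-specify sex and age group (18-20, 21-25) as fixed covariates, together with the baseline outcome, in the mixed model and the effect-size model.
- State that the effect size is standardised by an outcome SD not reduced by these covariates. With the residual SD as divisor, D would rise by the factor 1/√(1−R²), 2.6% at R² = 0.05 and 5.4% at 0.10, and would lose the Cohen's D reading that the plan intends.
- Report baseline balance descriptively, without significance tests as a trigger.
- Label any model whose covariates were chosen after seeing the data as a sensitivity analysis.

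The cost is a few sentences and two model degrees of freedom. Both factors are already collected, and at R² = 0 the loss of power is negligible (81.7% with or without them in step 3 of the working). Sample size does not change.

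### Adjustment or stratification is triggered by significant baseline differences between randomised arms; a short covariate list fixed in advance would be better, though the gain is modest

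*Combined protocol and SAP*

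**What the plan says.** The randomisation paragraph of the Aim 2 Methods names two balancing factors: "Randomization to conditions will be balanced based on sex and age (18-20, 21-25 years) using urn randomization in blocks of 4". For the efficacy outcomes, DSMP item 11 (Specific Aim 2) then says that "we will validate randomization by evaluating covariate balance between groups", and continues: "If significant differences that could confound treatment effect estimates emerge, we will adjust for those variables or stratify analyses".

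The paragraph on testing for intervention effects adds a second open trigger: "If we ascertain the need, we will control for confounders through their inclusion in the model as covariates". It gives no test, threshold, candidate list or timing, and no rule for choosing between adjustment and stratification.

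One covariate is fixed in advance, the baseline value of the outcome. It enters by subtraction in the first-listed test ("Our first choice will be a two-sample *t*-test to compare the pre-post differences between groups"), as a covariate at the 2-month visit in the mixed model ("Baseline adjustment at only the first follow-up (2M in this case) corrects this overestimation while also guarding against regression to the mean"), and in the model for the standardised effect size. In the efficacy analyses sex and age appear only as possible moderators, not as fixed covariates.

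**The concern.** Once arms are randomised, any baseline difference between them is due to chance. A significance test on it therefore asks a question whose answer is already known, and its result says nothing about whether the randomisation worked. It is also a poor guide to which covariates to use. What a covariate can do to the estimate depends on its imbalance multiplied by how strongly it predicts the outcome. The test sees only the imbalance, on a scale set by the sample size.

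Two things are at stake. Precision is given up whenever a useful predictor happens not to be flagged. In addition, the analysed model, including a possible split into strata of a trial of 102, is settled by chance and by an undated judgement of what could confound. The pilot's effect estimates are meant to inform a later trial, so it helps if the model behind them is known beforehand.

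**Working it through.** **Inputs from the documents.** Total enrolment of 102 ("Target enrollment is 102 EAs") in two arms of 50 to 52 (Aim 2, Enrollment); 51 per arm is used. The Power Analysis paragraph states power above 80% for D > 0.56 at a single time point.

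**Assumptions.** Two-sided 5% tests (alpha and sidedness are not stated), reading significant as a statistical test, complete follow-up, and all correlations, since the documents give none.

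**1. The plan's own figure.** The standard error of a standardised mean difference is √(2/51) = 0.198, and 0.56/0.198 = 2.83. Normal-approximation power is Φ(2.83 − 1.96) = 81%. For 50/51/52 per arm, power is 80.0/80.7/81.5% by the normal formula and 79.2/80.0/80.7% by the t-test. The stated figure reproduces to within a point.

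**2. What the rule can detect.** Significance requires a difference of t(0.975; 100) × √(2/51) = 1.984 × 0.198 = 0.39 SD. A chance imbalance above 0.25 SD in a given covariate has probability 2[1 − Φ(0.25/0.198)] = 0.207. Of this, 0.05 is flagged, so about 16% of trials carry an imbalance above 0.25 SD that the rule does not act on.

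**3. How often chance sets off the rule.** Each tested covariate is flagged in 5% of trials. The Measures table lists 27 measures taken at screening or baseline, counting PHQ-8 and GAD-7 separately and leaving out the two tailoring items. If all were tested and independent, P(at least one flag) = 1 − 0.95^27 = 75%, with 27 × 0.05 = 1.35 flags expected. Related measures lower the probability: at common pairwise correlations of 0.2, 0.3 and 0.5 it is about 70%, 64% and 49%. The plan does not say that all 27 would be tested, so this shows only that a chance flag would not be unusual.

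**4. Power given up beyond the baseline outcome.** The baseline outcome is always in the model (correlation 0.5), the true effect is 0.45 SD, and there is one further covariate with partial correlation r. With the baseline outcome alone, SE = √(1 − 0.5²) × 0.198 = 0.1715, and power is about Φ(0.45/0.1715 − 1.98) = Φ(0.64) = 74%. Adding a covariate with r = 0.3 gives SE = 0.1715 × √(1 − 0.3²) = 0.1636, and power of about Φ(2.75 − 1.98) = 78%. Simulation (30,000 trials per setting) gives:

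| Partial r | Under the rule | Covariate fixed in advance | Loss (points) |
|---|---|---|---|
| 0.1 | 73.7% | 73.9% | 0.2 |
| 0.2 | 73.7% | 74.8% | 1.1 |
| 0.3 | 73.7% | 77.2% | 3.5 |
| 0.4 | 74.2% | 80.2% | 6.0 |

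With no true effect, the rule rejects in 4.7 to 4.8% of these trials.

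**5. What happens when many variables are candidates.** Same model, true D = 0.5, 27 independent candidates of which one is prognostic (partial r = 0.3):

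| Approach | Power |
|---|---|
| No further covariate | 82% |
| Every flagged variable enters | 80% |
| Only a flagged prognostic variable enters | 82% |
| One covariate chosen in advance | 85% |

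Under the rule, simulated mean estimates were 0.498 to 0.506 for a true 0.50.

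**The case against.** The case for leaving the text alone is substantial. The plan does not select on significance alone: the difference must also be one that could confound. The baseline outcome, probably the strongest predictor, is used regardless. The efficacy analyses are exploratory, the primary outcomes are descriptive, and the effect-size model is described with the baseline measurement as its only covariate, so the rule need not touch it. All of this stands and limits the weight of the point. It does not supply a covariate list or say when the judgement is made, and the confounding qualifier cannot bring in a prognostic variable that falls below the significance threshold.

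Three stronger readings are tempting, and the documents do not support them.

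- A reader might infer that the rule is worse than adjusting for nothing further, because it admits variables selected for their association with arm. That holds (80% against 82%) only if the qualifier is ignored and every flagged variable enters. If only prognostic variables enter, the rule is about equal to no further covariate. Perfect filtering is itself an idealisation, so practice would probably lie between the two.
- A reader might infer that the estimate is biased. In trials with a missed imbalance above 0.25 SD, and with no baseline term in the model, it is off by about 0.09 SD (correlation 0.3) to 0.15 SD (correlation 0.5). The power loss in that no-baseline setting reaches 12 points at a correlation of 0.6. But every alcohol-outcome analysis in the plan uses the baseline outcome, so these figures belong to no planned model. Averaged over trials, the estimate is unbiased.
- A reader might infer a raised false-positive rate. Overall type I error stays near 5%.

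**Conclusion.** The point holds in a limited form. Significance between randomised arms is the wrong trigger for adjustment. It cannot validate the randomisation, and it leaves the model and the choice between adjusting and stratifying open until data are seen. The measurable cost is forgone precision: about 0 to 6 power points beyond the baseline outcome for partial correlations of 0.1 to 0.4, and about 3 points at 0.3. If non-prognostic flagged variables are let in as well, the rule can fall about 2 points below using no further covariate. These sizes rest on 51 analysed per arm, a two-sided 5% test, a baseline-outcome correlation of 0.5 and the assumed partial correlations; if the other predictors are weak, the loss is close to zero. Validity is not threatened and the primary outcomes are unaffected. This is an improvement worth considering, at most a low-priority recommendation.

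**What to change.** In DSMP item 11, replace the significance-triggered sentence under Specific Aim 2 and the covariate sentence under Testing for Intervention Effects ("If we ascertain the need, we will control for confounders through their inclusion in the model as covariates") with one statement, fixed before any follow-up data are seen. It should say that:

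- the efficacy models include the baseline outcome in the form already described, the balancing factors sex and age group, and at most one or two named baseline variables expected to predict the outcome;
- these covariates are included whatever the observed balance;
- baseline characteristics are shown by arm descriptively, without p-values, and not as a validation of the randomisation;
- no stratified analysis is triggered by an observed imbalance.

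The similar conditional wording about error distributions and random effects is a separate matter and is not touched by this change. The cost is two sentences and no new data. The downside is at most four degrees of freedom if the chosen covariates prove weak, out of 102 − 3 = 99 at a single time point after intercept, arm and baseline outcome.

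### Neither exploratory efficacy test fully removes chance baseline imbalance; entering the baseline value at both follow-ups in the planned joint model would do so at almost no cost

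*Combined protocol and SAP*

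**What the plan says.** The text is in DSMP item 11, Specific Aim 2, under Testing for Intervention Effects.

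- **Two-sample step.** Groups are first compared on HID frequency and consequences, "operating on the pre-post differences (e.g., 4M-Baseline) to test for treatment effects". A t-test is the first choice, with non-parametric alternatives if needed.
- **Joint mixed model.** The plan says "baseline adjustment is important for guarding against regression to the mean in RCTs", but warns that "such adjustment at every time point may overestimate the treatment effect when there are multiple follow-ups". It then states "Baseline adjustment at only the first follow-up (2M in this case) corrects this overestimation" and adopts that approach. The initial model is Gaussian with a random intercept only, and "the treatment effect is estimated by the treatment group indicator in the regression model". The plan concludes that "this approach is effectively the same as the ANCOVA method of RCT analysis", modified for multiple follow-ups.
- **Further adjustment.** The opening paragraph of Specific Aim 2 adjusts or stratifies only when significant group differences emerge. The model paragraph adds: "If we ascertain the need, we will control for confounders through their inclusion in the model as covariates".
- **Effect size.** Effect Size Estimation takes a standardized treatment coefficient "in a model adjusted for the baseline measurement", with no visit named.

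Randomization balances sex and age group only. In the measures table, HID before randomization is recorded at screening only.

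**The concern.** The plan gives protection against regression to the mean as its reason for adjusting, yet neither test delivers it in full. A change score subtracts the whole baseline difference, which is too much whenever the true slope is below 1. That is plausible here, because past-month HID is an entry criterion and its screening value is the only pre-randomization value. The mixed model, read literally, has no baseline term on the 4-month record, so at that visit it is not ANCOVA.

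With about 51 per arm, chance differences in baseline drinking are to be expected, and randomization does not balance on drinking. The two analyses then shift by different amounts and, with equal SDs, in opposite directions, so they can disagree for no reason connected with treatment. The effect size, which is meant to inform the next trial, comes from a baseline-adjusted model that is not tied to either test, so it too may disagree with them.

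**Working it through.** **Inputs from the documents.** 50-52 per group, total target 102 (51 per arm used here); D = 0.56 with power above 80% at a single time point (Power Analysis); Gaussian random-intercept model.

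**Assumed, because the documents do not give them.** Two-sided alpha 0.05; baseline-to-follow-up correlation r = 0.3, 0.5 or 0.7, the same at both visits; 2M-4M correlation equal to r unless stated; follow-up SD = 1 and baseline SD = k, with k = 1 unless stated; complete data.

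**The plan's own figure.** A two-sample t-test on a single outcome at D = 0.56 has power 79.2%, 80.0% and 80.7% for 50, 51 and 52 per arm. The stated 0.56 is reproduced.

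**Size of chance imbalance.** SE of the baseline difference = sqrt(2/51) = 0.198 SD. The probability of a difference beyond 0.2 SD in either direction is 0.31 per outcome. A significance trigger at p < 0.05 acts only beyond about 0.39 SD (t quantile × 0.198).

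**Change score against ANCOVA at one visit.** Var(change) = 1 + k² - 2rk; Var(ANCOVA) = 1 - r². The change-score estimate shifts by (r - k) × the imbalance in baseline SDs; ANCOVA does not shift.

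| r (k = 1) | Var change / ANCOVA | Power at D = 0.56, change / ANCOVA | Shift of change score at 0.2 SD |
|---|---|---|---|
| 0.3 | 1.40 / 0.91 | 65.8% / 83.5% | -0.14 |
| 0.5 | 1.00 / 0.75 | 80.0% / 89.9% | -0.10 |
| 0.7 | 0.60 / 0.51 | 95.1% / 97.5% | -0.06 |

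At r = 0.3 the effect detectable with 80% power by the change score is 0.66, not 0.56. The gap depends on k: at r = 0.5 the powers are 89.5% against 89.9% for k = 0.6, and 68.6% against 89.9% for k = 1.25.

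**Mixed model.** Simulation of the random-intercept REML model, 4,000 null trials per r. The slope is the change in the estimate per 1 SD of baseline imbalance.

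| r | Slope, single coefficient: 2M only / both visits | Slope, 4M group-by-time: 2M only / both | SD, single coefficient: 2M only / both |
|---|---|---|---|
| 0.3 | +0.19 / 0.00 | +0.30 / 0.00 | 0.155 / 0.150 |
| 0.5 | +0.34 / -0.01 | +0.48 / -0.02 | 0.157 / 0.142 |
| 0.7 | +0.58 / +0.02 | +0.72 / +0.02 | 0.168 / 0.120 |

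A 0.2 SD imbalance therefore moves the 2M-only single coefficient by +0.04, +0.07 and +0.12 SD, and the 4M group-by-time estimate by about +0.06, +0.10 and +0.14. At r = 0.5 with a 2M-4M correlation of 0.7, the single-coefficient slope is +0.43, a shift of +0.09. At the 0.39 SD trigger with r = 0.5, the shifts are about -0.20 (change score), +0.13 (single coefficient) and +0.19 (4M group-by-time).

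The variance ratio, both visits to 2M only, is 0.150²/0.155² = 0.94, 0.142²/0.157² = 0.82 and 0.120²/0.168² = 0.51. A separate run of 1,500 trials gave SDs of 0.160 and 0.119 at r = 0.7, a ratio of 0.55. Single-coefficient power for D = 0.56 at both visits (3,000 trials per r) is 95%, 94% and 92% with 2M only, against 96%, 97% and 99.6% with both.

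**The overestimation claim.** With baseline at both visits, null means were within 0.006 of zero, and a true 0.56 was estimated at 0.558 to 0.563. In another setting (r = 0.5, 2M-4M correlation 0.6) a true 0.40 was estimated at 0.403, with power 77% against 68% for 2M only.

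**Type I error.** The change-score test and the single-coefficient tests stay near 5%. In the group-by-time sub-analysis the 4M test rejects 5.8%, 6.3% and 8.4% of null trials with 2M-only adjustment (6.8%, 5.9% and 7.1% in the 1,500-trial run), against 4.9%, 5.2% and 5.3% with both visits.

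**The case against.** The strongest points on the other side are these.

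- *The t-test is a preliminary step.* It is preferred over non-parametric two-sample tests, not over the mixed model, and Power Analysis names the regression coefficient as the inferential target. This is fair: the largest power loss belongs to the opening comparison. The plan nevertheless uses that comparison to test for treatment effects and does not call it descriptive.
- *For the target coefficient the power gain is modest.* This stands at D = 0.56: 95/94/92% is already well above 80%. The large variance gain needs r near 0.7 at both visits; with 0.7 at 2M and 0.6 at 4M the ratio is 1/1.51 = 0.66. Sensitivity to imbalance remains.
- *The type I inflation is a variance-model effect.* Adjusting only 2M leaves residual variances of 1 - r² and 1, while the model assumes them equal; that alone predicts about 5.5/6.7/8.9%. Giving 4M its own variance restores about 5%, and the plan promises diagnostics. This stands. The inflation is confined to an exploratory sub-analysis, and adjusting at both visits removes its source.
- *The wording may be loose.* The ANCOVA sentence and the effect-size model point towards full adjustment. If that was the intention, the text needs correcting rather than the method.
- *The magnitudes rest on assumptions.* HID is truncated by eligibility, so equal SDs are doubtful. With k = 0.6 and r = 0.7 the change-score shift changes sign, so opposite directions is not a general result. No count model was simulated.

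None of this gives a reason to leave baseline out at 4 months.

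**Conclusion.** The concern holds as a matter of conditional error and precision, not of validity on average: over randomization all these estimators are unbiased and the main tests hold their level. With r between 0.3 and 0.7 and equal SDs, a one-standard-error baseline difference moves the change-score estimate by -0.14 to -0.06 SD and the 2M-only single coefficient by +0.04 to +0.12 SD. Adjustment at both visits brings this to about zero. The safeguards do not secure adjustment, because one waits for a significant difference and the other is discretionary. The stated reason for omitting baseline at 4 months found no support in the plan's own initial model.

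The mixed-model part depends on the literal reading, and every size depends on the assumed correlations, SD ratio, Gaussian outcomes and complete data. Efficacy is exploratory and the primary outcomes are descriptive, so this is a change that should be made rather than one on which the trial depends.

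**What to change.** - Keep the joint 2M/4M mixed model. Enter the baseline value of the outcome at both visits (baseline and baseline-by-time terms), with sex and age group, prespecified whatever any balance check shows.
- Take the test, confidence interval and effect size from that model. Let the overall treatment coefficient lead for each outcome, with the 2M and 4M coefficients in support.
- Label the change-score t-test descriptive.
- Delete the statement that adjusting at every time point overestimates the effect.
- If a Poisson or Negative Binomial model is chosen, keep the same baseline terms.
- Name the screening HID value as the HID baseline covariate.

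The cost is plan wording and one model line, using values already collected, with no added participants, visits or items. Statistically it takes one or two regression degrees of freedom. If baseline were unrelated to outcome (r = 0), the SD of the estimate would go from 0.176 to 0.177.
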